7.3.9 Columbia Suicide Severity Rating Scale (C-SSRS)

The Columbia Suicide Severity Rating Scale is a widely used and validated assessment of suicidal ideation and suicidal behavior (Posner 2011). It provides a structured interview to assess, over both lifetime and the past 6-months, several types of suicidal ideation and behavior,

stratified by risk for suicide completion. This will be used to assess suicide risk at screening and to monitor for an adverse event of increasing suicidality throughout the study. It will be administered at Office Visits 1, 3, and 5, and at Phone Visits 2 and 5.

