1.7 Study Timeline

Each subject's participation in this study will last 11-15 weeks. This includes a 1- to 5-week screening period (depending on the scheduling of the initial PSG), two 4-week treatment periods, and a 2-week washout period between the treatment periods.

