For all subjects who meet non-PSG eligibility criteria, the screening/baseline PSG will be completed within 3 weeks (0-21 days) after Office Visit 1. This will be performed at EvergreenHealth's Sleep Disorders Center according to their standard clinical protocol. At a minimum, PSG interpretation will report latency to persistent sleep (LPS), wakefulness after sleep onset (WASO), sleep efficiency, and apnea-hypopnea index (AHI). In addition to screening for eligibility, the screening PSG will provide baseline values for the PSG variables of interest. Eligibility will be confirmed based on the results of the PSG according to the eligibility criteria listed in section 5.1.

4.4 Treatment Period 1

4.4.1 Office Visit 2

For those who satisfy all eligibility criteria, Office Visit 2 will occur within 7-14 days after the screening PSG. Medications will be reviewed again to ensure stability of the PD medication regimen and absence of any prohibited medications.

Following confirmation of eligibility, an eligible patient will complete the baseline assessments of the MDS-UPDRS (only parts 1, 2, and 4; the data from part 3 that was collected at Office Visit 1 as a part of the screening will serve as the baseline for this measure), ISI, ESS, BDI, and BAI during Office Visit 2. Data from the wearable sleep monitor will be collected.

An eligible patient will be randomized in a 1:1 randomization scheme to receive suvorexant 10 mg qhs or placebo. Randomization will occur at the research pharmacy of EvergreenHealth using

a computer-generated randomization list. The pharmacist will maintain a codebook indicating the treatment allocation of each subject. Study medication will be delivered by the research pharmacist to the research study staff from the research pharmacy (a separate locked room containing only research medications). The investigating physicians, research coordinator(s), and study subjects will be blinded as to treatment arm until the code is broken. The randomization code may be broken by the investigator only in a medical emergency. The reasons for such an emergency will be documented carefully. The subjects will receive identical appearing active or placebo study medication tablets, with identification known only to the research pharmacist.

4.4.2 Phone Visit 1

Phone Visit 1 will occur 3-4 days after Office Visit 2 to review safety and tolerability through questioning about adverse events.

4.4.3 Phone Visit 2: Titration in Treatment Period 1

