11. APPENDIX

11.1 Schedule of Assessments

Appendix 11.1: Schedule of Assessments

	Visit 1: Screening	PSG 1	Visit 2: Start Treatment Period 1	Phone Visit 1	Phone Visit 2	Phone Visit 3	PSG 2	Visit 3: Start Washout Period	Visit 4: Start Treatment Period 2	Phone Visit 4	Phone Visit 5	Phone Visit 6	PSG 3	Visit 5: Final
Timing	Week 0	Week 3 (0-21 days post Visit 1)	Week 5 (7-14 days post PSG 1)	Week 5.5 (3-4 days post Visit 2)	Week 7 (12-15 days post Visit 2)	Week 7.5 (3-4 days post Phone Visit 2)	Week 9 (25-32 days post Visit 2)	Week 9 (0-7 days after PSG 2)	Week 11 (11-18 days post Visit 3)	Week 11.5 (3-4 days post Visit 4)	Week 13 (12-15 days post Visit 4)	Week 13.5 (3-4 days post Phone Visit 5)	Week 15 (25-32 days post Visit 4)	Week 15 (0-7 days after PSG 3)
Informed Consent	X													
Study Eligibility (inclusion/exclusion)	X		X											
Medical History	X													
Sleep History	X													
PD History	X													
Concomitant Medication and Allergy Review	X		X					X	X					X
Levodopa-equivalent daily dose calculation	X													
AE Assessment				X	X	*		X	X	X	X	*		X
Physical Exam	X							X						X
MDS-UPDRS, Part 3 (Motor Exam)	X													
MDS-UPDRS, Parts 1, 2, & 4			X											
MDS-UPDRS, full assessment								X	X					X
UK Brain Bank Criteria review	X													
Hoehn and Yahr Staging for Parkinson's	X													
Laboratory Testing (CBC, CMP, albumin, INR)	X							X (CBC, CMP)	*					X (CBC, CMP)
Assessment of Child-Pugh Score	X													
Pregnancy Testing (urine hCG)	**		**					**	**					**
Overnight Polysomnogram (Sleep Study), including analysis by sleep specialist		X						X						X
Calculation of Sleep Efficiency		X						X						X
Calculation of Waking after Sleep Onset (WASO)		X						X						X
Calculation of Latency to Persistent Sleep		X						X						X
Insomnia Severity Index			X					X	X					X
Epworth Sleepiness Scale			X					X	X					X
Montreal Cognitive Assessment (MoCA)	X							X	X					X
Beck Depression Inventory			X					X	X					X
Beck Anxiety Inventory			X					X	X					X
Columbia Suicide Severity Rating Scale	X				X			X			X			X
Clinician's Global Impression of Change of disease symptoms								X	X					X
Subject's Global Impression of Change of disease symptoms					X			X	X		X			X
Dispense wearable sleep monitor	X													
Upload data from wearable sleep monitor			X					X	X					X
Randomization			X											
Drug Dispensing			X					X (placebo)	X					

*As indicated

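### The only C-SSRS before treatment is 7-35 days old at randomization; a short repeat at Office Visit 2 would give suicidality arising during screening a check before the first dose

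*Combined protocol and SAP*

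**What the plan says.** On timing, section 7.3.9 states: "It will be administered at Office Visits 1, 3, and 5, and at Phone Visits 2 and 5". Section 7.1.6 attaches mandatory withdrawal to the four of those contacts that follow randomization. The C-SSRS row of the schedule (Appendix 11.1) marks the same five contacts. Office Visits 2 and 4, where the medication for each treatment period is dispensed (6.1), are not among them.

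Section 5.2 defines the suicidality exclusion by C-SSRS answers and anchors it to screening. It covers ideation over the past 6 months and suicidal behavior over the lifetime.

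For Office Visit 2, section 4.4.1 describes one re-check: "Medications will be reviewed again to ensure stability of the PD medication regimen and absence of any prohibited medications". It continues: "Following confirmation of eligibility, an eligible patient will complete the baseline assessments of the MDS-UPDRS" (parts 1, 2 and 4), together with "ISI, ESS, BDI, and BAI during Office Visit 2". Randomization follows. The schedule marks its eligibility row at Visit 1 and again at Visit 2.

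**The concern.** The C-SSRS carries both of the plan's suicidality rules: who may enter (5.2) and who must leave (7.1.6). Suicidality can change over weeks, and up to five weeks may pass between the screening interview and randomization. A subject who develops ideation in that interval could be randomized and take study medication for about two weeks before the plan's own instrument is used again.

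Nothing else scheduled at Office Visit 2 does the same job. As written, the BDI and MDS-UPDRS Part 1 come after eligibility has been confirmed, and neither has a suicidality threshold or a required action. The schedule marks no adverse event assessment at that visit. By contrast, two other exclusions that can change are looked at again: medications (4.4.1) and, in pre-menopausal women, pregnancy (7.1.3 and the schedule).

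What is at stake is subject safety at first dose. Sample size, type I error and the primary analysis are not involved.

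**Working it through.** The plan states no figure for these intervals, so they are built from its visit windows.

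**Inputs (days)**
- Office Visit 1 to PSG 1: 0-21 (4.3.2)
- PSG 1 to Office Visit 2: 7-14 (4.4.1)
- Office Visit 2 to Phone Visit 2: 12-15 (4.4.3)
- Office Visit 2 to PSG 2: 25-32 (4.4.5)
- PSG 2 to Office Visit 3: 0-7 (4.5)
- Office Visit 3 to Office Visit 4: 11-18 (4.6.1)
- Office Visit 4 to Phone Visit 5: 12-15 (4.6.3)

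**Age of the last C-SSRS when period medication is dispensed**
- Office Visit 2: (0 + 7) to (21 + 14) = 7-35 days. The schedule's labels, Week 0 and Week 5, give 35 days, the top of the range.
- Office Visit 4: 11-18 days.

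**Interval between successive C-SSRS administrations**

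| Interval | Calculation | Days |
|---|---|---|
| Office Visit 1 to Phone Visit 2 | (7 + 12) to (35 + 15) | 19-50 |
| Phone Visit 2 to Office Visit 3 | (25 + 0 - 15) to (32 + 7 - 12) | 10-27 |
| Office Visit 3 to Phone Visit 5 | (11 + 12) to (18 + 15) | 23-33 |
| Phone Visit 5 to Office Visit 5 | same windows as the second row | 10-27 |

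The first interval has the largest maximum in the plan. Its last 12-15 days are on study medication, if dosing begins at Office Visit 2.

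**Effect of adding Office Visit 2.** The 19-50 day interval splits into 7-35 and 12-15 days. The longest interval anywhere falls from 50 to 35 days, and the reading at randomization is 0 days old. The 12-15 days from dispensing to the Phone Visit 2 reading do not change.

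**Effect of also adding Office Visit 4.** The 23-33 day interval splits into 11-18 and 12-15 days. The longest interval after randomization falls from 33 to 27 days.

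**Subjects starting active drug.** With 1:1 allocation, 20 x 1/2 = about 10 at Office Visit 2 and about 10 at Office Visit 4.

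**Interviews.** Now 5 x 20 = 100. With Office Visit 2, 6 x 20 = 120. With both, 7 x 20 = 140.

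**The case against.** A reader might infer that the plan breaks its own rule by re-confirming eligibility at Office Visit 2 without the instrument that defines one criterion. The documents do not support that. Section 4.3.1 leaves the PSG-dependent criteria open at Office Visit 1, and 4.3.2 settles them from the PSG. The second eligibility mark is most naturally the completion of those criteria plus the medication review, and nothing says that every criterion is measured again. The exclusion is anchored to screening, as are the cognitive (MoCA) and hepatic (Child-Pugh) exclusions, and neither of those is re-measured at Office Visit 2.

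A reader might also infer that someone who meets the exclusion on the day of randomization would be enrolled against the protocol. That depends on what screening means. Section 4.3.1 equates it with Office Visit 1, in which case later suicidality is outside the criterion. Section 1.7 speaks of a screening period of 1 to 5 weeks, in which case it is inside, but the instrument is given only once. The plan does not settle this.

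The residual risk is also narrowed. Entrants have passed a 6-month ideation screen and a lifetime behavior screen. They are seen in person at Office Visit 2, called 3-4 days later, and may be withdrawn for safety at any time (5.4). When the C-SSRS is next given, 7.1.6 asks about behavior since the previous administration and about ideation worse than baseline, so the finding is late rather than missed.

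Finally, it is tempting to claim the same gap at Office Visit 4. That visit has no eligibility step, adverse events are assessed there, and its 11-18 days lie within the 10-27 days the plan accepts within a treatment period. Subjects who had active drug first go from washout placebo to placebo. What remains is that about 10 placebo-first subjects first receive suvorexant at that visit.

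All of this limits the weight of the point. It does not supply a check with an action rule between Office Visit 1 and the first dose.

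**Conclusion.** The point holds as a safety improvement of modest weight. It is not an inconsistency or a protocol error. The only pre-treatment C-SSRS precedes randomization by 7-35 days, and the next falls 12-15 days into dosing. Between them, nothing scheduled before the first dose would act on new suicidality.

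This rests on the stated windows being kept and on dosing starting at Office Visit 2. The documents give no rate of new suicidality during screening, so the number of subjects affected cannot be estimated. About half of those randomized start on placebo. The primary endpoint is unaffected.

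**What to change.** Give the since-last-administration C-SSRS at Office Visit 2, before randomization. Reword the suicidality exclusion so that it applies at screening or at Office Visit 2, which also removes the ambiguity over what screening means. Keep Office Visit 1 as the baseline for 7.1.6, so that worsening during screening does not raise the threshold for later withdrawal. Update 1.9.2, 4.4.1, 5.2, 7.3.9 and the schedule.

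The cost is about 20 extra short interviews (100 to 120), somewhat more if withdrawn subjects are replaced (5.4), and a slightly longer visit. The visit already takes place and the instrument is already in use.

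Adding the C-SSRS at Office Visit 4 before dispensing is optional. It would bring the total to 140 interviews and would need matching changes in 4.6.1 and 7.1.6.

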7.4 Efficacy Assessment Based on Wearable Sleep Monitor

The secondary outcome measure based on the wearable sleep monitor (WSM) will include:

- Total hours of sleep per night, mean over final 7 nights of treatment period compared to mean over final 7 nights of screening period
- Wakefulness after sleep onset (WASO), mean over final 7 nights of treatment period compared to mean over final 7 nights of screening period

8. Statistical Methods

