Phone Visit 2 will occur 2 weeks (12-15 days) after Office Visit 2 to review safety and tolerability through questioning about adverse events. The SGIC and C-SSRS will also be administered over the phone. Those subjects who report no AEs on suvorexant 10 mg po QHS (or matched placebo) and who report a persistent sleep disturbance will be titrated to suvorexant 15 mg po QHS (or matched placebo).

4.4.4 Phone Visit 3

Only for those subjects who are titrated to 15 mg, Phone Visit 3 will occur 3-4 days after Phone Visit 2 to review safety and tolerability through questioning about adverse events. For those who remain on 10 mg, Phone Visit 3 will not be conducted.

4.4.5 PSG 2

Overnight PSG 2 will occur after 4 weeks (25-32 days) after Office Visit 2 and will mark the last night of Treatment Period 1. Subjects will continue to take the study medication on the night of PSG 2. This will be performed at EvergreenHealth's sleep lab according to their standard clinical protocol. At a minimum, PSG interpretation will report latency to persistent sleep (LPS), wakefulness after sleep onset (WASO), and sleep efficiency.

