Phone Visit 5 will occur 2 weeks (12-15 days) after Office Visit 4 to review safety and tolerability through questioning about adverse events. The SGIC and C-SSRS will also be administered over the phone. Those subjects who report no AEs on suvorexant 10 mg po QHS (or matched placebo) and who report a persistent sleep disturbance will be titrated to suvorexant 15 mg po QHS (or matched placebo).

4.6.4 Phone Visit 6

Only for those subjects who are titrated to 15 mg, Phone Visit 6 will occur 3-4 days after Phone Visit 5 to review safety and tolerability through questioning about adverse events. For those who remain on 10 mg, Phone Visit 6 will not be conducted.

4.6.5 PSG 3

PSG 3 will occur 4 weeks (25-32 days) after Office Visit 4 and will mark the last night of Treatment Period 2. Subjects will continue to take the study medication on the night of PSG 3. This will be performed at EvergreenHealth's sleep lab according to their standard clinical protocol. At a minimum, PSG interpretation will report latency to persistent sleep (LPS), wakefulness after sleep onset (WASO), and sleep efficiency.

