8.5 Efficacy Analysis

Analysis of primary and secondary outcome measures will include:

- Summary statistics (n, mean, standard deviation, median, minimum and maximum) at baseline, Office Visit 3 and Office Visit 5 by treatment.
- For clinical rating scales, summary of % change from baseline to Office Visit 3, from baseline to Office Visit 5, and from Office Visit 4 to Office Visit 5, by treatment
- For PSG variables, summary of % change from PSG 1 to PSG 2 and from PSG 1 to PSG 3, by treatment

- For wearable sleep monitor, summary of % change in total hours of sleep and WASO. Mean over the week prior to Office Visit 2 (baseline) will be compared to the mean over the final week of Treatment Period 1 and to the mean over the final week of Treatment Period 2. Mean over the week prior to Office Visit 4 (during washout) will be compared to the mean over the final week of Treatment Period 2. This will be done by treatment arm.
- Significance testing

Outcome measures will be compared between groups using analysis of covariance (ANCOVA) or other method as deemed appropriate by the consulting statistician. Demonstration of superiority will depend on achieving statistical significance for the primary endpoint. Level of significance will be defined as $p = 0.05$. All statistical tests will be two-sided.

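### The wearable's last treatment week always contains a laboratory PSG night and its comparison weeks almost never do, so within-arm changes carry an unmatched lab-night term of one seventh

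*Combined protocol and SAP*

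**What the plan says.** Sections 1.10.4 and 7.4 define both wearable outcomes (total hours of sleep and WASO) as "mean over final 7 nights of treatment period compared to mean over final 7 nights of screening period". Sections 1.11 and 8.5 then ask for percentage changes by treatment arm. The baseline is the week before Office Visit 2, and it is set against the final week of each treatment period. For Treatment Period 2 there is a further comparison: "Mean over the week prior to Office Visit 4 (during washout) will be compared to the mean over the final week of Treatment Period 2".

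The visit schedule fixes where the laboratory nights fall:

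- PSG 1 takes place "within 3 weeks (0-21 days) after Office Visit 1" (section 4.3.2), and "Office Visit 2 will occur within 7-14 days after the screening PSG" (section 4.4.1).
- PSG 2 "will mark the last night of Treatment Period 1" (section 4.4.5).
- PSG 3 "will mark the last night of Treatment Period 2" (section 4.6.5).
- Office Visit 3 is 0-7 days after PSG 2, and Office Visit 4 is 11-18 days after Office Visit 3 (sections 4.5 and 4.6.1, and the Schedule of Assessments).

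The monitor is to be worn throughout (section 1.5) and to record every night (section 4.3.1). PSG nights are included, because a secondary hypothesis compares the two devices on those nights (sections 1.6.2 and 3.4). No section excludes PSG nights from the weekly wearable means or adjusts for them.

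**The concern.** A PSG night differs from a home night by design. The subject sleeps in the sleep laboratory and must avoid alcohol, caffeine and marijuana for 6 hours beforehand and overnight, and nicotine during the recording (section 5.1). If the wearable records different sleep on such a night, a week that contains one is not like a week that does not.

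At stake are the within-arm wearable changes, which is how the protocol itself words these outcomes. A lab-night difference would appear as a change from baseline even on placebo with no true change, and it would add to or subtract from the change on drug. Section 1.11 says any treatment effect might be used to power a later, larger study, so a within-arm change taken at face value could mislead.

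**Working it through.** **The plan's own figure.** The only stated figure that follows from these windows is the screening length in section 1.7. Its limits are (0 + 7)/7 = 1 week and (21 + 14)/7 = 5 weeks. Adding 4 + 2 + 4 weeks gives 11 to 15 weeks in total. Both match the protocol, so the windows are being read as intended.

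**Treatment weeks.** The PSG is the last night of each period, so the final 7 nights always include it. Its share is 1/7 = 14.3%.

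**Baseline week.** Let Office Visit 2 be d days after the PSG 1 evening, with d = 7 to 14. Calling the PSG 1 night 0, the week before the visit covers nights d - 7 to d - 1. Night 0 is included only when d = 7, which is 1 of 8 permitted offsets. If days are counted from the morning on which the PSG ends, it is 0 of 8.

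**Washout week.** Office Visit 4 is a + b days after PSG 2, with a = 0 to 7 and b = 11 to 18. The minimum is 11, so the week before the visit starts no earlier than night 11 - 7 = 4 after PSG 2. The PSG night is included in 0 of 8 × 8 = 64 combinations.

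**Size of the term.** Let L be the laboratory night minus a home night for the measure in question, and T the true mean change at home.

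- Treatment week minus a week of 7 home nights = T + L/7.
- As a percentage of a baseline B, the lab-night part is 100 × L/(7B).
- When d = 7 and L is the same at both PSGs, the change from baseline has L/7 - L/7 = 0.

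The documents give no L. For total sleep, as an assumption, with B = 360 minutes also assumed:

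| Assumed absolute L (min) | Shift L/7 (min) | % of 360 min |
|---|---|---|
| 0 | 0 | 0 |
| 15 | 2.1 | 0.6 |
| 30 | 4.3 | 1.2 |
| 60 | 8.6 | 2.4 |

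WASO has a term of the same form with its own L. Nothing in the documents allows a size to be put on it. If the PSG night is recorded but some home nights are not, the weight rises from 1/7 to 1/k for k recorded nights.

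**Drug minus placebo.** Both treatment weeks end on a PSG night. With true changes T_d on drug and T_p on placebo, (T_d + L/7) - (T_p + L/7) = T_d - T_p, so a common L drops out. If the lab-night effect differs between drug and placebo by I, then I/7 remains; an assumed I of 30 minutes would leave 4.3 minutes.

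**Illustration.** Assume L = -45 minutes, T_d = +20 and T_p = 0. Then L/7 = -6.4, the drug change reads 20 - 6.4 = +13.6, the placebo change reads -6.4, and the difference is still 20. Without PSG nights the changes read +20 and 0. A simulated crossover under the same assumptions gave +13.5, -6.5 and 20.0 with the PSG night, and +20.0, -0.1 and 20.1 without it.

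**The case against.** The strongest reply is that this is a placebo-controlled crossover, so the treatment effect is the drug-placebo comparison, and the same 7-night window applies under both treatments. That stands. A reader might infer that the laboratory night is confounded with treatment; the documents do not support this, because both periods end on a PSG night and a common effect cancels. Nor is superiority at risk: section 8.5 ties it to the primary endpoint, PSG sleep efficiency, which uses no wearable data.

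It can also be said that no bias has been shown. That stands too: neither the size nor the direction of L is in the documents, and zero is possible. A reader might carry a total-sleep figure over to WASO, but nothing supports doing so.

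A reader might further infer that the baseline mix, varying between subjects, adds material noise. At most 1 of 8 offsets brings PSG 1 into that week. In a completed crossover, both of a subject's changes from screening share the same baseline week, so its make-up drops out of the within-subject difference in absolute change.

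Finally, the shift is small against sampling error. With an assumed SD of change of 45 to 60 minutes and 20 subjects, the standard error is 45/√20 = 10.1 to 60/√20 = 13.4 minutes, larger than 8.6. That limits its importance but does not remove it, since a systematic term does not average out over subjects. The window is clear and reproducible as written; the point is that it is not matched to its comparison weeks.

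**Conclusion.** The point holds for the within-arm changes in wearable total sleep and WASO from the screening or washout week, and for nothing beyond them. Each carries an unmatched L/7, apart from changes from baseline in subjects whose Office Visit 2 is exactly 7 days after PSG 1. For total sleep the shift is 0 to 8.6 minutes if |L| is 0 to 60 minutes; that range is an assumption and the direction is unknown. No size can be given for WASO. The timing rests on the protocol's own windows and on the monitor being worn on PSG nights, which the agreement hypothesis requires. The drug-placebo contrast is not biased by a common lab-night effect. These are secondary outcomes in an exploratory pilot, so this is a minor but free improvement.

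**What to change.** Exclude PSG nights from all wearable weekly means:

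- For each treatment period, average the last 7 home nights before PSG 2 or PSG 3.
- For baseline and washout, keep the week before Office Visit 2 or Office Visit 4, and leave out the PSG 1 night if it falls in that week. These weeks cannot be anchored to a PSG as the treatment weeks are: PSG 1 may fall 0 days after Office Visit 1, when the monitor is only just dispensed, and no PSG ends the washout.
- Use PSG nights only for the wearable-versus-PSG agreement analysis.

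Make the same change in sections 1.10.4, 1.11, 7.4 and 8.5, so that synopsis and body agree. The cost is one sentence in each place, with no new visit or data collection, because the monitor already records every night. Moving the treatment window back one night keeps it after the titration call: the earliest PSG is day 25 after the visit that opens the period, so the window starts no earlier than day 25 - 7 = 18, and the call is at day 12-15.
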